**VERSION DATE: 04/16/2021****STUDY SUMMARY:**

Investigational Agent(s) (Drugs or Devices)	N/A
IND / IDE / HDE #	
Indicate Special Population(s)	 Children  Children who are wards of the state  Adults Unable to Consent  Cognitively Impaired Adults  Neonates of Uncertain Viability  Pregnant Women  Prisoners (or other detained/paroled individuals)  Students/Employees
Sample Size	Prospective study: 25 Subjects  Retrospective study (historical controls): 25 subjects
Funding Source	Department of Ophthalmology  Illinois Society for the Prevention of Blindness
Indicate the type of consent to be obtained	 Written  Verbal/Waiver of Documentation of Informed Consent  Waiver of HIPAA Authorization  Waiver/Alteration of Consent Process

STU00213080

Site	 Lead Site ( For A Multiple Site Research Study)  Data Coordinating Center (DCC)
Research Related Radiation Exposure	 Yes  No
DSMB / DMC / IDMC	 Yes  No

**OBJECTIVES:**

The aim of the research is to assess the surgical success, feasibility and utility of pre-operative Anterior Segment Optical Coherence Tomography (AS-OCT) and intraoperative Optical Coherence Tomography (iOCT) in trans-conjunctival needle revision (TCNR) of trabeculectomy bleb. Furthermore, we want to assess whether AS-OCT can be used to identify characteristics of trabeculectomy blebs that are associated with successful surgical outcomes.

To undergo this study, we will conduct a prospective study of patients who consent to AS-OCT and iOCT revision of TCNR. We will compare the outcomes of these patients with retrospectively identified, historical controls (i.e. patients who underwent TCNR by the same surgeon without AS-OCT or iOCT assistance).

We hypothesize that information gained from pre-operative AS-OCT and intraoperative OCT will aid with intraoperative decision-making for TCNR of trabeculectomy bleb and will thereby improve surgical outcomes. We also hypothesize that preoperative AS-OCT can be used to identify features of trabeculectomy bleb that can predict success with iOCT-assisted TCNR. More specifically, we hypothesize that filtering blebs with more extensive scarring as seen on pre-operative AS-OCT will benefit from iOCT.

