**STUDY ENDPOINTS:**

STU00213080

Results from the following tests obtained as part of this study:

1. Spectralis Anterior-segment OCT (AS-OCT) (Heidelberg Engineering) available in Lavin 15th floor Ophthalmology clinic
2. Digital microscope integrated with Intraoperative OCT (Zeiss Artevo 800, Carl Zeiss Meditec AG) available in the Lavin 11th floor operating room

The primary outcome will be surgical success, defined as a 20% reduction in unmedicated IOP below the pre-operative baseline at the post-operative visits (POD1, POM1, POM3). The success rate will be compared to a cohort of historical controls comprised of a consecutive series of age- and race-matched subjects who underwent TCNR in the operating room by the same surgeon, with the same intraoperative anti-fibrotic therapy, without AS-OCT or iOCT imaging during a five-year time period from 6/1/2015 to 6/1/2020.

The secondary outcomes will be feasibility and utility of intraoperative OCT. Feasibility will be defined as the percentage of cases with successful imaging of the bleb with iOCT. Utility will be defined as the percentage of cases in which iOCT changed surgical decision-making.

Intraoperative OCT will be used to determine whether adhesions have been completely lysed and/or whether further lysis of adhesions is necessary. A survey with set of questions based on prior literature will be used to assess these parameters.

We will also assess whether findings seen with pre-operative AS-OCT can predict what type of blebs will benefit from iOCT-assisted TNCR. Features of AS-OCT and iOCT imaging that will be assessed include quality of image capture, visualization of surgical site, and characteristics of the bleb. Characteristics of the surgical site include bleb height, internal reflectivity, location and number of adhesions, and presence of cysts, cavities, and fistulas.

STU00213080

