**STUDY INTERVENTION(S) / INVESTIGATIONAL AGENT(S):**

This prospective study will include approximately 25 patients with open-angle glaucoma who will undergo TCNR or trabeculectomy bleb by a glaucoma specialist at Northwestern Medicine. These patients will have a history of glaucoma and failed trabeculectomy bleb (as evidenced by clinical features and elevated IOP). During routine clinic visit, the patient will undergo lit lamp grading of bleb by Indiana Bleb Appearance Grading Score (IBAGS). Subjects who agree to participate and provide written informed consent will undergo AS-OCT imaging (Spectralis OCT, Heidelberg) of the bleb. During their operation, the Zeiss Artevo digital microscope integrated with iOCT (Zeiss Artevo 800, Carl Zeiss Meditec AG), a commercially available device will be utilized to visualize and evaluate the morphology of the trabeculectomy bleb at the start and conclusion of the case.

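### The design cannot show which blebs benefit from iOCT: no planned eye has AS-OCT without iOCT, so only prognosis and utility by AS-OCT feature can be estimated

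*Protocol*

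**What the plan says.** The Objectives section gives two hypotheses about pre-operative AS-OCT. The first is that it can identify bleb features that "predict success with iOCT-assisted TCNR". The second is introduced as more specific: "we hypothesize that filtering blebs with more extensive scarring as seen on pre-operative AS-OCT will benefit from iOCT". Study Endpoints then plans to assess whether AS-OCT findings can "predict what type of blebs will benefit from iOCT-assisted TNCR", and lists the bleb characteristics to be used: "bleb height, internal reflectivity, location and number of adhesions, and presence of cysts, cavities, and fistulas". Benefit is not defined in either section.

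On who is imaged, Study Intervention(s) says of the prospective group: "Subjects who agree to participate and provide written informed consent will undergo AS-OCT imaging". In the same patients' operations the iOCT microscope "will be utilized to visualize and evaluate the morphology of the trabeculectomy bleb at the start and conclusion of the case". Study Endpoints defines the historical controls as treated "without AS-OCT or iOCT imaging during a five-year time period". Objectives and Procedures Involved also describe controls as managed without either technique.

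Study Endpoints has a separate secondary outcome: "Utility will be defined as the percentage of cases in which iOCT changed surgical decision-making".

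**The concern.** Saying that a type of bleb benefits from iOCT, in the ordinary sense of a better surgical result, is a claim about a difference: success with iOCT minus success without it, among eyes of that type. Predicting which blebs benefit means asking whether this difference varies with the AS-OCT feature. That needs outcomes with and without iOCT in eyes whose AS-OCT features are known. The planned groups supply only the first half.

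The prospective arm alone shows which blebs do well or badly after iOCT-assisted revision. That is prognosis, and it can point the opposite way from benefit. Heavily scarred blebs may do worse than others with iOCT and still gain most from it, because they would have done worse again without it. As the protocol stands, a prognostic association in 25 eyes could be reported as evidence on which blebs iOCT helps.

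**Working it through.** The protocol states no success rate, effect size or power for this aim, so there is no figure to reproduce. The question is whether the quantity can be estimated at all.

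**Planned cells** (from Study Summary, Study Endpoints and Study Intervention(s))

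| | iOCT used | iOCT not used |
|---|---|---|
| AS-OCT features known | 25 | 0 |
| AS-OCT features not known | 0 | 25 |

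**Identifiability.** Let S be the AS-OCT feature and T the use of iOCT. A model for differential benefit has columns 1, S, T and S×T. Where S is known, T is always 1, so column T equals column 1 and column S×T equals column S. The rank is 2 of 4. The S×T term, which is the differential benefit, cannot be separated from the S term at any sample size.

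**Target quantity**

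Differential benefit = (success with iOCT, more − fewer) − (success without iOCT, more − fewer)

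The second bracket is never observed.

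**Illustration.** All counts are assumed. Number of adhesions stands in for extent of scarring.

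- Prospective eyes: success in 6/12 with more adhesions and 9/13 with fewer.
- Controls: success in 12/25 overall, with the same 12/13 split by adhesions, which nobody can see.

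First bracket: 50.0 − 69.2 = −19.2 points. This is the estimable prognostic difference. Its Newcombe 95% interval is −49.8 to +17.2.

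| Unseen control split (more; fewer) | Gain, more | Gain, fewer | Differential benefit |
|---|---|---|---|
| 3/12; 9/13 | 50.0 − 25.0 = +25.0 | 69.2 − 69.2 = 0 | +25.0 |
| 6/12; 6/13 | 50.0 − 50.0 = 0 | 69.2 − 46.2 = +23.1 | −23.1 |

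Both rows add to 12/25 in controls and leave the prospective data unchanged. The observable data are identical and the conclusions opposite.

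**Logical limits.** If 0/12 and 12/13 controls succeed, the result is −19.2 − (0 − 92.3) = +73.1. If 12/12 and 0/13 succeed, it is −19.2 − (100 − 0) = −119.2. These extremes are not plausible values; they show only that the data do not bound the answer usefully.

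**Package contrast.** Prospective eyes have AS-OCT plus iOCT and controls have neither, so the gains above are gains from the combination. Even a known control split would not isolate iOCT.

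**Precision if the empty cell were filled.** Suppose AS-OCT existed for all 25 controls, with four cells of 12.5 eyes and about 50% success in each. The standard error of the differential benefit is √(4 × 0.25/12.5) = 0.28, and the 95% half-width is 1.96 × 0.283 = 0.55, or about 55 points.

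**The case against.** The strongest reply is that benefit need not mean a gain over surgery without iOCT. The disputed sentence follows directly on a prognostic one and is offered as a refinement of it. The Study Endpoints wording could mean doing well after the assisted procedure, or having a case in which iOCT changed the decision. Both can be estimated in the prospective eyes, and the protocol announces no interaction test. This stands as far as it goes: the difficulty applies to the gain-in-success reading only. But that reading is natural, since the same paragraph of Objectives expects the imaging to improve surgical outcomes and the sentence before already covers prognosis. A word that admits one reading the design cannot support should be defined or replaced.

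Second, Objectives and Procedures Involved describe controls as lacking imaging assistance rather than imaging, and Procedures Involved calls AS-OCT routine. Some controls might therefore have a scan on file. Study Endpoints is stricter and excludes imaging outright, and nothing plans to retrieve such scans. Prospective eyes in which iOCT imaging fails are no substitute either: they are unplanned and selected by the failure itself.

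Third, the aim is supplementary and would be very imprecise here even with complete data. That is true, and it limits the importance of the point. It does not make the claim estimable. An analysis plan could define benefit as success or utility, but could not recover outcomes by a feature that is not recorded in controls.

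**Conclusion.** The concern holds. Read as a gain in surgical success, benefit from iOCT by AS-OCT feature is not identified under the stated design, because 0 of 50 planned eyes have AS-OCT without iOCT. This rests on the control definition in Study Endpoints and the imaging of all prospective eyes in Study Intervention(s); it does not depend on the assumed counts, which only show that the answer can change sign on the same data.

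The reach is limited. The comparison of success with historical controls, the feasibility outcome and the overall utility outcome are planned and computed as before, although the first compares AS-OCT plus iOCT with neither. What changes is what may be concluded from the supplementary AS-OCT analysis: prognosis and utility by feature, each with wide intervals. The correction should be made, but the trial does not turn on it.

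**What to change.** 1. Replace the benefit sentences in Objectives and Study Endpoints with a prognostic statement, for example: *In eyes treated with iOCT-assisted TCNR, we will examine which of the AS-OCT features listed under Study Endpoints, such as adhesion count and internal reflectivity, are associated with surgical success. This is a prognostic analysis.*
2. Add a separate analysis of utility, already defined under Study Endpoints, tabulated across the same AS-OCT features. Call it utility, not benefit.
3. State that no conclusion will be drawn on whether the gain from iOCT differs by AS-OCT feature.
4. Report both analyses with confidence intervals.

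The cost is two reworded sentences and one small table from data already being collected, with no added patients, visits or imaging. The price is a more modest claim. Keeping the benefit question would instead require a comparator with AS-OCT and no iOCT, and at about 25 eyes per group the answer would still carry a half-width of roughly 55 points under the assumptions above.

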**BACKGROUND:**

Trabeculectomy is one of the most commonly performed glaucoma procedures performed to control IOP with approximately 18,000 operations performed in US Medicare beneficiaries

STU00213080

alone in 2012. One complication of trabeculectomy surgery is the formation of subconjunctival and episcleral fibrosis, which occurs as part of the wound healing process and can result in fibrosis of the filtering bleb and failure. Transconjunctival needle revision (TCNR) aims to lyse subconjunctival adhesions and reestablish adequate aqueous humor flow from the anterior chamber to the subconjunctival space. One study reported 17% of trabeculectomies require bleb-needling revision. During TCNR the surgeon is able to visualize the trajectory of the needle or blade under the conjunctiva; however, detection of the fibrotic tissue and determination as to whether that tissue has been adequately lysed is difficult, limiting the success rate of the procedure.

Anterior segment optical coherence tomography (AS-OCT) allows for detailed assessment of the internal morphology of the bleb. Studies have utilized AS-OCT to assess morphological features of the bleb and correlate it with surgical success. A small case series reported the utility of AS-OCT for pre-operative planning for bleb revision, in particular, identifying safe access sites and minimizing conjunctival dissection.

More recently, real time OCT integrated with operative microscope has become available. Intraoperative OCT (iOCT) has been utilized extensively in retinal surgery and corneal surgery. Dada et al., described performing iOCT-guided TCNR in 2 patients with failed trabeculectomy blebs without intraoperative or postoperative complications. These authors report they were able to obtain a detailed view of the bleb wall and assess the depth and location of the needle, which permitted better lysis of adhesions. A pilot study by Kumar et al., reported one case of TCNR in which iOCT was used to demonstrate the extent of adhesions and loculations inside the bleb at the beginning of the procedure, and the lysis of these adhesions and formation of large single hyporeflective cavity inside the bleb at the end of the procedure. These small case studies suggest a role of iOCT imaging for TCNR, however, further research is needed to assess its feasibility and utility for routine use.

**STUDY ENDPOINTS:**

STU00213080

Results from the following tests obtained as part of this study:

1. Spectralis Anterior-segment OCT (AS-OCT) (Heidelberg Engineering) available in Lavin 15th floor Ophthalmology clinic
2. Digital microscope integrated with Intraoperative OCT (Zeiss Artevo 800, Carl Zeiss Meditec AG) available in the Lavin 11th floor operating room

The primary outcome will be surgical success, defined as a 20% reduction in unmedicated IOP below the pre-operative baseline at the post-operative visits (POD1, POM1, POM3). The success rate will be compared to a cohort of historical controls comprised of a consecutive series of age- and race-matched subjects who underwent TCNR in the operating room by the same surgeon, with the same intraoperative anti-fibrotic therapy, without AS-OCT or iOCT imaging during a five-year time period from 6/1/2015 to 6/1/2020.

The secondary outcomes will be feasibility and utility of intraoperative OCT. Feasibility will be defined as the percentage of cases with successful imaging of the bleb with iOCT. Utility will be defined as the percentage of cases in which iOCT changed surgical decision-making.

Intraoperative OCT will be used to determine whether adhesions have been completely lysed and/or whether further lysis of adhesions is necessary. A survey with set of questions based on prior literature will be used to assess these parameters.

We will also assess whether findings seen with pre-operative AS-OCT can predict what type of blebs will benefit from iOCT-assisted TNCR. Features of AS-OCT and iOCT imaging that will be assessed include quality of image capture, visualization of surgical site, and characteristics of the bleb. Characteristics of the surgical site include bleb height, internal reflectivity, location and number of adhesions, and presence of cysts, cavities, and fistulas.

STU00213080

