**PROCEDURES INVOLVED:**

The devices used in the study are commercially available and have been used extensively in ophthalmology and intraocular surgery. Therefore, no experimental devices will be used. The AS-OCT is routinely obtained and is considered standard of care. The iOCT is commercially available and is also utilized routinely in ophthalmic surgery, particularly for retinal surgery.

The Zeiss Artevo digital microscopy integrated with intraoperative OCT will be used as an adjunct to TCNR. Published research has not shown iOCT to increase risk of complications associated with routine TCNR and we believe injury from imaging is not biologically plausible. Surgery and iOCT will be recorded and saved to a secure NMH server. The surgical videos will only be used for research purposes.

Review of medical records will be performed for patients who agree to participate in the prospective study. Data gathered will include basic demographic information and clinical data relevant to glaucoma management (visual acuity, intraocular pressure, medications, disease

STU00213080

severity). Post-operative course including intraocular pressure, intraoperative or post-operative complications and repeat TCNR or additional surgery will also be collected.

Furthermore, a retrospective review of medical records will be performed for patients who underwent TCNR without iOCT or AS-OCT assistance by the same surgeon during the period from June 1, 2015 to June 1, 2020. This group of patients will serve as historical controls. These individuals will be identified using Enterprise Data Warehouse and billing data. We aim to identify approximately 25 controls. The selection criteria for controls are 1) age within 5 years of each study patient 2) same race as study patient 3) diagnosis of open angle glaucoma and 4) adequate follow up of at least 3 months.

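### Utility counts decisions that iOCT changed, but the protocol requires no record of the surgeon's judgement before either scan is seen

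*Protocol*

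**What the plan says.** Utility is one of two secondary outcomes in the Protocol, Study Endpoints: "Utility will be defined as the percentage of cases in which iOCT changed surgical decision-making". The same section names the decision that the image is meant to inform: "Intraoperative OCT will be used to determine whether adhesions have been completely lysed and/or whether further lysis of adhesions is necessary". It gives the instrument for feasibility and utility as "A survey with set of questions based on prior literature", with a literature reference. The questions are not reproduced, and the text does not say who answers them or when.

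Study Intervention(s) says when the image is used, namely to "visualize and evaluate the morphology of the trabeculectomy bleb at the start and conclusion of the case". Procedures Involved describes the microscope as "integrated with intraoperative OCT will be used as an adjunct to TCNR", so the operating team sees the images and may act on them. The same section adds: "Surgery and iOCT will be recorded and saved to a secure NMH server". It does not connect these recordings to the utility outcome.

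The Objectives state the expected result. Imaging "will aid with intraoperative decision-making for TCNR of trabeculectomy bleb and will thereby improve surgical outcomes".

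**The concern.** Whether iOCT changed a decision can be known only by comparing what the surgeon would have done without the image with what was done after seeing it. The second is observable. The first exists only in the surgeon's mind, and only until the image appears. If it is not fixed at that moment, the answer becomes an after-the-fact account of what would otherwise have happened, given by someone who has seen the image and works on a study that expects imaging to help.

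The Background says that judging whether fibrotic tissue has been adequately lysed is difficult. A hard judgement is a poor one to reconstruct afterwards.

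Two features add to the weight of the point. Utility has no comparison group, because the historical controls had no iOCT, so no contrast within the study could reveal misattribution. And this is a matter of data collection: an analysis plan cannot recover a judgement that was never recorded.

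**Working it through.** The protocol states no target rate, precision or power for utility, so there is no planned figure to reproduce. The check is first a reading of the text and then an illustration of scale.

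**Step 1: what the definition needs and what is collected.**

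| Needed to establish a change | Where the Protocol deals with it |
|---|---|
| Judgement before the opening scan | Not required in any section |
| Judgement after the opening scan | Possibly the survey; timing not stated |
| Judgement before the concluding scan (lysis complete or not) | Not required in any section |
| Judgement after the concluding scan | Possibly the survey; timing not stated |
| Who judges | Not stated |
| What counts as a change | Not stated beyond the definition of utility |
| Independent or masked review | Not described; recordings exist but are not linked to utility |

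The opening scan matters as much as the concluding one. It is seen before needling begins, so the plan without iOCT is also lost unless it is noted first.

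**Step 2: weight of one case.** The denominator comes from Study Intervention(s): "This prospective study will include approximately 25 patients with open-angle glaucoma". One case is 1/25 = 4 percentage points.

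**Step 3: how misattribution carries through.** Let *t* be the true proportion of cases changed, *f* the share of unchanged cases reported as changed, and *g* the share of changed cases reported as unchanged. Then

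reported utility = *t*(1 − *g*) + (1 − *t*)*f*.

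The documents give none of these values. Those below are assumptions, shown as a range and in both directions.

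| True *t* | Over-reporting only (*g* = 0): *f* = 10%, 20%, 30% | Under-reporting only (*f* = 0): *g* = 10%, 20%, 30% |
|---|---|---|
| 0% | 10%, 20%, 30% | 0%, 0%, 0% |
| 10% | 19%, 28%, 37% | 9%, 8%, 7% |
| 20% | 28%, 36%, 44% | 18%, 16%, 14% |
| 40% | 46%, 52%, 58% | 36%, 32%, 28% |

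As a count: with *t* = 20%, 5 of 25 cases are truly changed and 20 are not. If *f* = 10%, 2 of those 20 are reported as changed, giving 7/25 = 28%.

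**Step 4: what a confidence interval would show.** Exact (Clopper-Pearson) 95% intervals are 6.8% to 40.7% for 5/25 and 21.1% to 61.3% for 10/25. They describe sampling error only. An interval around a misattributed count is centred in the wrong place and gives no sign of it.

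**The case against.** The strongest reply is that the survey cannot be seen. The protocol does assign an instrument, based on published work, and that form may already contain paired items before and after each scan. This stands in part: it cannot be said that the study will fail to capture the prior judgement. What can be said is that the protocol does not require it, and that one of its named outcomes depends on it.

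A reader might infer several stronger things that the documents do not support.

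- *That utility rests on an unmasked operator's memory.* No respondent is named and recall is not mentioned. The operating surgeon is the most likely respondent, since only that person can say what would otherwise have been done, but this is inference. The recordings also mean that some contemporaneous material will exist.
- *That utility is biased upwards by a known amount.* The hypothesis in the Objectives makes upward error plausible. But a surgeon looking back may also conclude that the same step would have been taken anyway, which lowers the figure. The second half of the table in Step 3 shows this case. Direction and size are both open.
- *That utility is the study's main evidence for routine use.* The Background names feasibility and utility for routine use as an open question, but the primary outcome is IOP-based surgical success against historical controls. Utility is one of two secondary percentages, with no threshold or decision rule attached.

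It can also be said that a paired item is not free of bias: a surgeon who knows that a scan follows may declare lysis complete sooner. That is fair. The paired record still replaces an unobservable comparison with an observed one.

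**Conclusion.** The point holds in a limited form. The protocol defines utility as a change but does not require the judgement from which change is measured to be recorded, at either of the two scans. Unless the survey already contains a pre-scan item, the outcome will be attributed after the image has been seen.

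The only size that follows from the documents is 4 percentage points per misattributed case, taking the planned 25 cases as the denominator. The larger shifts in the working depend on assumed error rates and illustrate scale; they are not estimates. That the operating surgeon answers is a reasonable assumption, not a stated fact. Feasibility and the primary IOP outcome are unaffected.

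The change should be made before enrolment proceeds, because the missing judgement cannot be recovered once an operation is over. If the survey already contains the paired items, stating so in the protocol settles most of the point.

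**What to change.** Add one paired item at each iOCT view, on the survey form or spoken on the surgical recording already planned.

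- **Before the opening scan is displayed:** the surgeon records the planned approach and the site of adhesions. The same item is repeated straight after the scan.
- **Before the concluding scan is displayed:** the surgeon records *lysis complete* or *further lysis needed*, and where. The same item is repeated straight after the scan.

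Define utility as the percentage of all operated cases in which the pre-scan and post-scan answers differ at either scan, and also report the two scans separately. Covering both scans matters: an item at the concluding scan alone would count any change of plan prompted by the opening scan as no change, and so would understate utility as the protocol defines it. State in the protocol who completes the items and that they are completed at the time. The saved recordings could also support a masked review, but this is optional.

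The cost is a few seconds in theatre at each scan, with no extra visit, staff or procedure. The utility figure may be lower than one obtained by asking afterwards. The change concerns recording only and sets no rule for how the surgeon should proceed.
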